3.3 Randomization

This is a non-randomized study. Patient assignment will be performed via Interactive Response Technology (IRT). Prior to the initiation of the study treatment, the site staff will contact the IRT in order to assign the subject to treatment. Specific procedures for assignment, enrollment and registration through the IRT are contained in the study procedures manual.

4 SAMPLE SIZE

This is an open-label, single arm study. No interim analysis and 1 final analysis are planned.

Phase 1

The sample size in phase 1 is based on 3+3 design and not based on power calculation. Up to 12 subjects will be enrolled in cohorts of 3 to 6 subjects to determine the RP2D following the dose levels of the combination treatment outlined in [Table 2](#).

Phase 2

Simon's 2-stage design [Simon, 1989] will be used in the study to evaluate the efficacy in terms of CRc rate for the selected combination dose level of gilteritinib and atezolizumab. The null hypothesis that the true CRc rate is 50% will be tested against a 1-sided alternative. In the first stage, the CRc of 22 subjects will be evaluated. If there are 11 or fewer subjects with CRc from these 22 subjects by the end of cycle 2, the study will be stopped. Otherwise, 27 additional subjects will be accrued for a total of 49 subjects evaluable for calculation of CRc rate. The null hypothesis will be rejected if 32 or more subjects with CRc are observed in the 49 subjects by the end of cycle 2. This design yields a 1-sided type I error rate of 0.025

and power of 80% when the true CRc rate is 70%. The sample size was calculated in East[®] Version 6.4.

5 ANALYSIS SETS

Detailed criteria for analysis sets will be laid out in Classification Specifications and the allocation of subjects to analysis sets will be determined prior to database hard-lock.

5.1 Full Analysis Set (FAS)

The full analysis set (FAS) will consist of all subjects who are enrolled in the study and took at least 1 dose of study drug. The FAS will be used for efficacy analyses. Subjects will be analyzed based on the actual treatment received.

5.2 Safety Analysis Set (SAF)

For the statistical summary of the safety data, the safety analysis set (SAF) will be used. The SAF consists of all subjects who took at least 1 dose of study drug (gilteritinib or atezolizumab) and will be used for safety analyses. The subjects will be analyzed based on the actual treatment received. The FAS and SAF are the same for this study.

5.3 Pharmacokinetics Analysis Set (PKAS)

The pharmacokinetics analysis set (PKAS) consists of the administered population for which sufficient plasma concentration data is available to facilitate derivation of at least one pharmacokinetic parameter and for whom at least 1 plasma concentration datum is available and both the date and time of dosing on the day of pharmacokinetic sampling and the date and time of sampling are known. Additional subjects may be excluded from the PKAS at the discretion of the pharmacokineticist. Any formal definitions for exclusion of subjects or time-points from the PKAS will be documented in the in the Classification Specifications and determined the Classification Meeting.

5.4 Biomarker Analysis Set (BMAS)

The biomarker analysis set (BMAS) will include the subjects from the administered population for whom sufficient biomarker measurements were collected.

6 ANALYSIS VARIABLES

6.1 Efficacy Endpoints

Efficacy analysis will be conducted on the FAS.

6.1.1 Primary Efficacy Endpoint

Composite complete remission (CRc) rate is the primary efficacy endpoint. The definition will be defined in Section [6.1.4](#).

6.1.2 Secondary Efficacy Endpoint

- Complete remission (CR) rate
- CR with partial hematologic recovery (CRh) rate

- Duration of remission
- Best response rate
- Event-free survival (EFS)
- Overall survival (OS)

The definition of secondary efficacy endpoint will be defined in Section 6.1.3 and Section 6.1.4.

6.1.3 Response Definition

Response to treatment will be defined per modified Cheson criteria [2003] as outlined below.

- Complete Remission (CR)

For subjects to be classified as being in CR, they must have bone marrow regenerating normal hematopoietic cells and achieve a morphologic leukemia-free state and must have an ANC $> 1 \times 10^9/L$ and platelet count $\geq 100 \times 10^9/L$, and normal marrow differential with $< 5\%$ blasts, and they must be red blood cell (RBC) and platelet transfusion independent (defined as 1 week without RBC transfusion and 1 week without platelet transfusion prior to disease assessment). There should be no evidence of extramedullary leukemia.

- Complete Remission with Incomplete Platelet Recovery (CRp)

For subjects classified as being in CRp, they must achieve CR except for incomplete platelet recovery ($< 100 \times 10^9/L$).

- Complete Remission with Incomplete Hematological Recovery (CRi)

For subjects to be classified as being in CRi, they must fulfill all the criteria for CR except for incomplete hematological recovery with residual neutropenia $< 1 \times 10^9/L$ with or without complete platelet recovery. RBC and platelet transfusion independence is not required.

- Composite Complete Remission (CRc)

For subjects to be classified as being in CRc at a post-baseline visit, they must either achieve CR, CRp or CRi at the visit.

- Complete Remission with Partial Hematological Recovery (CRh)

For subjects classified as being in CR, except if their ANC is $> 0.5 \text{ Gi/L}$ and their platelets are $> 50 \text{ Gi/L}$.

- Partial Remission (PR)

For subjects to be classified as being in PR, they must have bone marrow regenerating normal hematopoietic cells with evidence of peripheral recovery with no (or only a few regenerating $\leq 2\%$) circulating blasts and with a decrease of at least 50% in the percentage of blasts in the bone marrow aspirate/biopsy with the total marrow blasts between 5% and 25%.

- Relapse

Relapse after CR, CRp or CRi is defined as a reappearance of leukemic blasts in the peripheral blood or $\geq 5\%$ blasts in the bone marrow aspirate/biopsy not attributable to any other cause or reappearance or new appearance of extramedullary leukemia.

Relapse after PR is similarly defined with reappearance of significant numbers of peripheral blasts ($>2\%$) or an increase in the percentage of blasts in the bone marrow aspirate/biopsy to $> 25\%$ not attributable to any other cause or reappearance or new appearance of extramedullary leukemia.

- Best Response

Best response is defined as the best-measured response (CR, CRp, CRi or PR) post-treatment. Two best responses, up to the time of 2 cycles of treatment period and the EOT Visit will be defined.

- Treatment Failure

Treatment failure is defined as lack of CR, CRp or CRi, and is determined at the EOT.

6.1.4 Definition of Other Efficacy Variables

- CR rate - Defined as the number of subjects with CR divided by the number of subjects in the analysis population. Subjects with unknown or missing response, or who provide no information on response at the end of study will be treated as non-responders and will be included in the denominator when calculating rates.
- CRp rate, CRi rate, CRh rate, PR rate – Defined similarly as CR rate.
- Best response rate – Defined as the number of subjects with CR or CRp or CRi or PR divided by the number of subjects in the analysis population (i.e., CR+ CRp + CRi + PR). Subjects with unknown or missing response, or who provide no information on response at the end of study will be treated as non-responders and will be included in the denominator when calculating rates.
- Duration of remission – This includes duration of CRc, duration of CR, duration of CR/CRh, and duration of response (CRc + PR) by the EOT.
 - Duration of CRc – Defined as the time from the date of either first CRc until the date of documented relapse of any type for subjects who achieve CRc. Subjects who die without report of relapse are considered non-events and censored at their last relapse-free disease assessment date. Subjects who come off study for an allogeneic HSCT will be considered nonevents and censored at the time of HSCT. Other subjects who do not relapse on study are considered non-events and censored at the last relapse-free assessment date.
 - Duration of CR, and CR/CRh – Defined similarly as duration of CRc.
 - Duration of response – Defined as the time from the date of either first CRc or PR until the date of documented relapse of any type for subjects who achieve CRc or PR. Subjects who die without report of relapse are considered nonevents and censored at their last relapse-free disease assessment date. Subjects who come off study for an

allogeneic HSCT will be considered nonevents and censored at the time of HSCT.

Other subjects who do not relapse on study are considered nonevents and censored at the last relapse-free assessment date.

- Event-free survival (EFS) – The time from the date of first dose until the date of documented relapse from CR, CRp or CRi, treatment failure or death from any cause, whichever occurs first.
 - If a subject experiences relapse or death the subject is defined as having an EFS event related to either “relapse” or “death,” and the event date is the date of relapse or death.
 - If a subject who discontinues the treatment due to treatment failure during the first 2 treatment cycles, and the subject has no previous response of CR, CRp or CRi, the subject is defined as having an EFS event and the event date is the date of first dose.
 - If a subject who discontinues the treatment due to treatment failure after the 2 treatment cycles, and the subject has no previous response of CR, CRp or CRi, the subject is defined as having an EFS event and the event date is the date of end of the 2nd treatment cycle evaluation date (i.e., cycle 3/day 1 bone marrow evaluation).
 - For a subject who is not known to have relapse or treatment failure or death, EFS is censored at the date of last relapse-free assessment date. Subject is not censored at HSCT.
- Overall survival (OS) - The time from the date of first dose until the date of death from any cause. For a subject who is not known to have died by the end-of-study follow-up, OS is censored at the date of last contact. Date of last contact is defined as the death date or the latest of the following dates: treatment discontinuation date, last dosing administration date, last disease assessment date or the last follow-up date on which the subject was known to be alive.

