During phase 1, DLT assessment will occur during cycle 1 only. AEs (toxicities) will be graded according to the CTCAE version 5.0.

Interim analyses:

No interim analysis is planned.

V. FLOW CHARTS AND SCHEDULE OF ASSESSMENTS

Phases 1 and 2

AML: acute myeloid leukemia; EOT: end of treatment; FLT3: FMS-like tyrosine kinase 3; q2w: every 2 weeks; RP2D: recommended phase 2 dose.

Table 1 Schedule of Assessments

Assessments	Screening	C1D1	C1D8 ^a	C1 D15 ^a	Subsequent Cycles D1	Subsequent Cycles D15 ^a	EOT ^b	30-Day Follow-up	Long-term Follow-up ^c
Windows	Day -14 to -1		± 1d				± 7d	+ 7d	± 7d
Signed ICF	X								
Medical and Disease History	X								
Enrollment		X							
Physical Examination ^d	X	X	X	X	X	X	X		
Vital Signs	X	X	X	X	X	X	X		
ECOG Performance Status ^e	X	X		X	X	X	X		
12-lead ECG ^f	X	X	X	X	X	X	X		
Chest X-ray (or CT of chest)	X								
Pregnancy Test for WOCBP ^g	X	X			X		X		
MUGA or ECHO	X								
Clinical Laboratory Tests (chemistry, hematology, coagulation, urinalysis) ^{h,i}	X ^h	X ^{h,i}	X ⁱ	X ⁱ	X	X	X		
Thyroid Function Test ^j	X				X ^j		X ^j		
Resource utilization		X			X		X		
FLT3 Mutation Status ^k	X ^k								
Bone Marrow Biopsy and/or Aspiration for disease assessment and MRD ^l	X ^l				X ^l		X ^l		
Pharmacokinetic Sample Collection ^m		X	X	X	X	X			
Blood Sample for FLT3 and AXL ⁿ		X							
Blood Sample for Immune Cell Immunophenotyping ^o		X		X	X ^o		X		
Blood Sample for Blast Cell Immunophenotyping ^o		X		X	X ^o		X		
PGx (whole blood and buccal swab) ^p		X							
AE/SAE Assessment	X	X	X	X	X	X	X	X ^q	X ^r
Prior and Concomitant Medications ^s	X	X	X	X	X	X	X	X ^r	
Survival and subsequent anti-leukemic treatments and their outcomes								X ^q	X
Gilteritinib Dosing at the Clinic ^t		X	X	X	X	X			
Subject Diary for Gilteritinib ^u		X			X				
Atezolizumab Dosing at the Clinic		X		X	X	X			

Footnotes appear on next page

AE: adverse event; CT: computed tomography; D: day; ECG: electrocardiogram; ECHO: echocardiogram; ECOG: Eastern Cooperative Oncology Group; EOT: end of treatment; FLT3: FMS-like tyrosine kinase 3; ICF: informed consent form; MRD: minimal residual disease; MUGA: multigated acquisition scan; PGx: pharmacogenomics; QTcF: Fridericia-corrected QT interval; SAE: serious adverse event; WOCBP: women of childbearing potential.

- a. Visits should be scheduled based on day 1.
- b. If subject permanently discontinues treatment, an EOT Visit should be conducted within 7 days of last dose of study drug.

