Subjects will be administered treatment until discontinuation criterion is met. If 1 treatment is discontinued due to toxicity, the subject may continue on the other as monotherapy until discontinuation criteria is met. Subjects will have an (EOT) visit within 7 days after last dose of study drug, followed by a 30-day follow up for safety, after which the subjects will enter the long-term follow-up period of up to 3 years for collection of subsequent AML treatment, remission status and survival (cause of death and date of death).

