5.3 Efficacy Assessments

5.3.1 Bone Marrow Aspirate and Biopsy

Bone marrow samples will be collected at screening, cycle 2/day 1 and cycle 3/day 1. For subjects who do not achieve a CR, CRp or CRi, the bone marrow assessments will be repeated on day 1 of every 2 subsequent cycles. For subjects who achieve a CRc (CR, CRp or CRi), bone marrow will be repeated 1 month after the date of remission and every 3 subsequent cycles or if there is suspicion of relapse in the whole blood. Bone marrow samples are also required at the EOT Visit and as clinically indicated. If bone marrow aspirate is unobtainable due to technical difficulties such as dry tap, a tube of whole blood (ethylenediaminetetraacetic acid [EDTA]) along with bone marrow biopsy should be collected instead. Remaining bone marrow aspirate and/or whole blood samples will be used for MRD analysis and may be used for other biomarker analyses in relation to treatment outcomes [described in Section 5.7] If bone marrow aspirate is unobtainable at relapse (e.g., dry tap), a peripheral blood smear should be collected along with bone marrow biopsy lab. All samples will be sent to the central lab. Refer to the laboratory manual for additional details.

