- Subject receives any antileukemic therapy (including HSCT) other than the assigned treatment, with the exception of hydroxyurea up to 5 g daily for up to 2 weeks, prophylactic intrathecal chemotherapy or cranial irradiation.
- Subject has not achieved a PR or CRc, and in the opinion of the investigator, is no longer deriving clinical benefit after 6 cycles of therapy.
- Investigator/subinvestigator determines that the continuation of the study treatment will be detrimental to the subject.
- Subject is lost to follow-up despite reasonable efforts by the investigator to locate the subject.
- Female subject becomes pregnant.
- Death
- Subject is receiving gilteritinib, atezolizumab, or the combination of gilteritinib + atezolizumab and has progressive disease, recurrence under treatment, or no response, and in the opinion of the investigator the subject is no longer deriving clinical benefit.

Discontinuation criteria from long term follow-up for individual subjects:

- Subject declines further study participation (i.e., withdraws consent)
- Subject is lost to follow-up despite reasonable efforts by the investigator to locate the subject.
- More than 3 years has passed from the EOT Visit.
- Death

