2 FLOW CHART AND VISIT SCHEDULE

phases 1 and 2

AML: acute myeloid leukemia; EOT: end of treatment; FLT3: FMS-like tyrosine kinase 3; q2w: every 2 weeks; RP2D: recommended phase 2 dose.

Table 1 Schedule of Assessments

Assessments	Screening	C1D1	C1D8 ^a	C1 D15 ^a	Subsequent Cycles D1	Subsequent Cycles D15 ^a	EOT ^b	30-Day Follow-up	Long-term Follow-up ^c
Windows	Day -14 to -1		± 1d				± 7d	+ 7d	± 7d
Signed ICF	X								
Medical and Disease History	X								
Enrollment		X							
Physical Examination ^d	X	X	X	X	X	X	X		
Vital Signs	X	X	X	X	X	X	X		
ECOG Performance Status ^e	X	X		X	X	X	X		
12-lead ECG ^f	X	X	X	X	X	X	X		
Chest X-ray (or CT of chest)	X								
Pregnancy Test for WOCBP ^g	X	X			X		X		
MUGA or ECHO	X								
Clinical Laboratory Tests (chemistry, hematology, coagulation, urinalysis) ^{h,i}	X ^h	X ^{h,i}	X ⁱ	X ⁱ	X	X	X		
Thyroid Function Test ^j	X				X ^j		X ^j		
Resource utilization		X			X		X		
FLT3 Mutation Status ^k	X ^k								
Bone Marrow Biopsy and/or Aspiration for disease assessment and MRD ^l	X ^l				X ^l		X ^l		
Pharmacokinetic Sample Collection ^m		X	X	X	X	X			
Blood Sample for FLT3 and AXL ⁿ		X							
Blood Sample for Immune Cell Immunophenotyping ^o		X		X	X ^o		X		
Blood Sample for Blast Cell Immunophenotyping ^o		X		X	X ^o		X		
PGx (whole blood and buccal swab) ^p		X							
AE/SAE Assessment	X	X	X	X	X	X	X	X ^q	X ^r
Prior and Concomitant Medications ^s	X	X	X	X	X	X	X	X ^r	
Survival and subsequent anti-leukemic treatments and their outcomes								X ^q	X
Gilteritinib Dosing at the Clinic ^t		X	X	X	X	X			
Subject Diary for Gilteritinib ^u		X			X				
Atezolizumab Dosing at the Clinic		X		X	X	X			

AE: adverse event; CT: computed tomography; D: day; ECG: electrocardiogram; ECHO: echocardiogram; ECOG: Eastern Cooperative Oncology Group; EOT: end of treatment; FLT3: FMS-like tyrosine kinase 3; ICF: informed consent form; MRD: minimal residual disease; MUGA: multigated acquisition scan; PGx: pharmacogenomics; QTcF: Fridericia-corrected QT interval; SAE: serious adverse event; WOCBP: women of childbearing potential.

Footnotes continued on next page

- ^a Visits should be scheduled based on day 1.
- ^b If subject permanently discontinues treatment, an EOT Visit should be conducted within 7 days of last dose of study drug.
- ^c Telephone contact every 3 months, from the date of the 30-day follow up visit additional contacts may be made to support key analyses. Subjects will be followed for up to 3 years after the 30-day follow-up visit.

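### EFS counts deaths through up to 3 years of follow-up but, on the natural reading, stops crediting event-free responders at about end of treatment, so the late curve is biased downward

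*SAP*

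**What the plan says.** EFS is a secondary endpoint, summarised by a Kaplan-Meier curve and median (SAP 7.4.2). Its events are documented relapse, "treatment failure or death from any cause, whichever occurs first" (SAP 6.1.4). Nothing limits when a death counts.

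For a subject without an event, SAP 6.1.4 and protocol 5.3.3.3 give the same rule: "EFS is censored at the date of last relapse-free assessment date. Subject is not censored at HSCT".

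The data behind that rule come from these places:

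- Protocol 6.1 lists among the reasons for withdrawal from study treatment: "Subject receives any antileukemic therapy (including HSCT) other than the assigned treatment".
- For subjects who stop, "an EOT Visit should be conducted within 7 days of last dose of study drug" (SAP Section 2, Table 1 footnote).
- "Bone marrow samples are also required at the EOT Visit and as clinically indicated" (protocol 5.3.1). Table 1 marks no marrow at the 30-day or long-term follow-up.
- After EOT there is telephone contact every 3 months, and "Subjects will be followed for up to 3 years after the 30-day follow-up visit". The Table 1 row for that period reads "Survival and subsequent anti-leukemic treatments and their outcomes".
- Protocol 2.2.1 and SAP 3.2.1 describe a "long-term follow-up period of up to 3 years for collection of subsequent AML treatment, remission status and survival".

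Neither document defines a relapse-free assessment after EOT. Neither says whether remission status obtained by telephone or from site records is one, or whether a relapse learned of that way is documented.

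**The concern.** Take two responders transplanted in remission at month 3. One dies at month 12 and is an EFS event at month 12. The other is alive in remission at month 24. If the last relapse-free assessment is the EOT marrow, that subject is censored at about month 3. Whether a subject stays in the risk set after transplant then depends on whether they later die. Kaplan-Meier needs censoring that is unrelated to the future outcome, and this is the opposite.

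The same applies to a responder who stops in remission for an adverse event or by choice. The subjects who do best leave the denominator early while the deaths remain, so the tail of the curve falls too fast, and falls further the more responders leave treatment in remission. EFS is also one of the outcomes against which MRD is to be assessed (SAP 7.4.3, protocol 7.8).

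**Working it through.** The documents state no EFS rate, event count or power, so there is no planned figure to reproduce. The check is first of wording, then of size.

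**Wording.** Three comparisons favour reading the term as a disease assessment.

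1. For responders who do not relapse on study, protocol 5.3.3.4 censors duration of CRc at the last relapse-free *disease* assessment. SAP 6.1.4 gives the same rule without the word *disease*. The two phrases are used interchangeably.
2. The OS rule names the last disease assessment and the last follow-up contact as separate dates. The EFS rule has no follow-up-contact element.
3. Relapse is defined by blasts in blood or marrow, or by extramedullary leukemia, which a telephone call does not measure.

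**Size in transplanted responders.** Assumptions: 20 responders, HSCT and last marrow at month 4, deaths evenly spaced from month 6 to month 24, the rest alive and relapse-free. Kaplan-Meier: S(t) = ∏(1 − dᵢ/nᵢ). If survivors are followed, 20 are at risk. If they are censored at month 4, only those who will die are at risk.

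| Deaths | 12 months, followed | 12 months, censored at month 4 | 24 months, followed | 24 months, censored at month 4 |
|---|---|---|---|---|
| 4 | 18/20 = 90% | 2/4 = 50% | 16/20 = 80% | 0/4 = 0% |
| 8 | 17/20 = 85% | 5/8 = 62.5% | 12/20 = 60% | 0/8 = 0% |
| 12 | 16/20 = 80% | 8/12 = 66.7% | 8/20 = 40% | 0/12 = 0% |

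Under censoring, the 12-month figure rises as deaths rise, which reverses the true order.

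**Size in the whole cohort.** Simulation of 200,000 subjects per scenario, all rates assumed:

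- CRc 55%; non-responders fail at day 0 or day 57, half each.
- Responders without transplant have a median of 5 months to event, counted from day 57.
- 20%, 40% or 60% of responders are transplanted at months 3 to 6, with 40%, 60% or 80% event-free 2 years later.
- Half of post-HSCT events are relapse first, with death on average 5 months after.
- Data cutoff at months 18 to 39.

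Each cell gives EFS with survivors followed / with survivors censored at EOT and only deaths captured after HSCT.

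| Transplanted | Event-free 2 years after HSCT | 6 months | 12 months | 24 months |
|---|---|---|---|---|
| 20% | 40% | 0.352 / 0.347 | 0.191 / 0.168 | 0.073 / 0.035 |
| 20% | 80% | 0.357 / 0.343 | 0.210 / 0.156 | 0.112 / 0.032 |
| 40% | 60% | 0.398 / 0.383 | 0.268 / 0.200 | 0.160 / 0.046 |
| 60% | 40% | 0.437 / 0.431 | 0.304 / 0.253 | 0.169 / 0.059 |
| 60% | 80% | 0.450 / 0.423 | 0.361 / 0.224 | 0.285 / 0.055 |

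Over all nine scenarios the shortfall runs:

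- at 12 months, from 0.191 − 0.168 = 0.023 to 0.361 − 0.224 = 0.137;
- at 24 months, from 0.073 − 0.035 = 0.038 to 0.285 − 0.055 = 0.230.

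Both curves are already below 50% by month 6, where the gap is at most 0.450 − 0.423 = 0.027, so the median barely moves.

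If relapses reported after EOT also count as events but survivors are still censored at EOT, the bias remains: EFS is 0.155 to 0.237 at 12 months and 0.032 to 0.056 at 24 months. If recorded continued remission extends EFS time, the second figure in each cell becomes the first and the bias is gone.

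**The case against.** The strongest reply is that the plan already intends to follow these subjects. Protocol 2.2.1 and SAP 3.2.1 list remission status among the long-term follow-up data. Protocol 5.3.3.1 collects subsequent treatments, including HSCT, and their outcomes for all subjects, and allows site records to supplement the calls. The HSCT sentence, set beside the explicit censoring at HSCT for duration of remission, shows that time after transplant is meant to count for EFS. On this view only a definition is missing.

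Much of that stands. A reader might infer that nothing about remission is known after EOT, or that the bias is certain. The documents support neither. What remains is that the EFS rule does not bring the collected status in, and its wording points the other way. Table 1 has no explicit remission item, and a responder who stops for an adverse event and takes no further therapy has no treatment outcome to report. Two programmers could follow the text and produce different curves.

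A reader might also take the transplant-only figures (0% against 40% to 80%) as what the trial would report. It would not: SAP 7.8 plans no subgroups. In the whole cohort the smallest gaps lie inside sampling error. With 49 subjects and true EFS of 0.09 to 0.16, the 95% half-width 1.96·√(p(1 − p)/49) is 0.08 to 0.10. The larger gaps exceed it, and a bias does not average out. The SAP plans no landmark EFS rates, but it does plan the curve.

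Two details soften the data flow. Marrows may be done when clinically indicated. Protocol 5.1.2.1 also has wording that seems to allow resumption of treatment after HSCT, while 6.1 makes HSCT a reason for withdrawal. Those passages should be reconciled, but neither supplies a scheduled assessment after EOT.

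**Conclusion.** The point holds as a gap in the EFS rule with a real consequence under its most natural reading. On that reading, responders who leave treatment in remission are events if they die and are censored near EOT if they live. That contradicts the statement that HSCT does not censor EFS, and it biases the late part of the curve downward.

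The size is illustrative, about 2 to 14 points at 12 months and 4 to 23 points at 24 months. It rests on assumed transplant shares, post-transplant outcomes and a 55% CRc rate. A higher CRc rate would move the median later, where the gap is wider. The simulation covers transplant only, not responders who stop in remission for other reasons.

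EFS is secondary and descriptive. The CRc decision rule is untouched, and OS already credits survivors to last contact. The change should be made, but the main conclusion of the trial does not depend on it.

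**What to change.** - In SAP 6.1.4 and protocol 5.3.3.3, state that for EFS the last relapse-free assessment includes the latest follow-up contact or site record at which continued remission is recorded. State also that a relapse recorded there counts as a documented relapse on its reported date.
- In Table 1 of both documents, add remission status and date of relapse to the long-term follow-up row, in line with protocol 2.2.1 and SAP 3.2.1.

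The cost is a few sentences and at most one item in a call that already takes place every 3 months. The eCRF is not among the documents, so the item may already exist. The downside is that remission status by telephone or site record is less precise than a marrow, and the relapse date is only as good as the report.

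A tempting alternative is to count a death only if it falls within one planned marrow interval of the last relapse-free assessment. This is not advised. It contradicts the any-cause definition, and no marrow interval is planned after EOT. It also reverses the bias. Take 10 responders with a last marrow at month 3, 4 deaths at month 12 and 6 in remission at month 24. The longest planned interval is 3 cycles (84 days), so all 4 deaths drop out and EFS reads 100%, against a true 6/10 = 60%.
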